10.13 Data and Safety Monitoring

Audits and Inspections

Authorized representatives of Duke University Health System (DUHS), the Institutional Review Board (IRB), and Cancer Protocol Committee (CPC) may perform audits or inspections, including source data verification. The purpose of such an audit or inspection is to systematically and independently examine study-related activities and documents to determine whether these activities were conducted, and data were recorded, analyzed, and accurately reported according to the protocol, Good Clinical Practice (GCP), guidelines of the International ICH, and any applicable regulatory requirements.

Study Monitoring Requirements

This study will be monitored by the sponsor-investigator and will be independently monitored and assessed in accord with the Duke Cancer Institute (DCI), NCI-approved Data and Safety Monitoring Plan.

In terms of internal review, the sponsor-investigator is responsible for monitoring the protocol to ensure that the investigation is conducted in accordance with the

general investigational plan and protocol (21 CFR 312.50), and all applicable regulatory requirements. The sponsor-investigator will continuously monitor and tabulate adverse events and will also monitor the conduct, data, and safety of this study to ensure that:

- *Interim analyses occur as scheduled;*
- *Stopping rules for toxicity and/or response are met;*
- Risk/benefit ratio is not altered to the detriment of the subjects;
- Appropriate internal monitoring of adverse events and outcomes is done;
- Over-accrual does not occur;
- Under-accrual is addressed with appropriate amendments or actions;
- Data are being appropriately collected in a reasonably timely manner.

External review begins with the initial scientific review by the CPC. The CPC assigns the degree of monitoring to commensurate with the type of intervention, phase, endpoints, degree of risk, size, and complexity of the protocol. The primary site, Duke, will be monitored by the DCI Safety Oversight Committee and the DCI Monitoring Team. The minimum level of monitoring to be determined by the DCI Monitoring Team may include the following: routine monitoring after the first 3 subjects have been enrolled, followed by annual monitoring of 1-3 subjects until closed to enrollment or subjects are no longer receiving study drug or other interventions that are more than minimal risk. Additional monitoring may be prompted by findings from monitoring visits, unexpected frequency of serious and/or unexpected toxicities, or other concerns. CPC conducts annual progress reviews focusing on protocol prioritization, accrual and scientific progress while the study is open to enrollment, excluding pediatric protocols.

DUMC will serve as the coordinating site for this multi-site study.

The DUHS sponsor-investigator is responsible for providing data and safety monitoring oversight for participating external sites. The Duke Gynecologic Oncology team will be monitoring the external sites. A site monitoring visit will be planned after the first 3 subjects are enrolled. If a physical site visit is logistically impossible, a copy of redacted source documents will be obtained from the external site and the subject data will be monitored by designated personnel. Subsequent monitoring will be arranged based on pace of accrual, accrual status, and results of previous monitoring.

[figure not shown]
The DCI Safety Oversight Committee (SOC) will conduct annual data and safety monitoring. SOC reviews data provided by the sponsor-investigator pertaining to safety data, toxicities and new information that may affect subject safety or efficacy. All safety concerns are communicated to the sponsor-investigator and will be communicated to the IRB and CPC as necessary.

10.14 Management Forms

The Duke Cancer Institute IT (DCI-IT) group will be responsible for the management of clinical data utilizing the caBIG-compliant platform, known as the Cancer Central Clinical Database (C3D), with local implementation at Duke. C3D is the Clinical Trials Database and a key component of NCI's Clinical Trial Suite (CTS). Oracle Clinical serves as the foundation of C3D by supporting clinical trial definition, data capture, multiple site reporting, data definition, and usage standardization. Trial definition is based on Common Data Elements (CDE) from an existing library of template Case Report Forms. Oracle Clinical's RDC Onsite system provides a user-friendly HTML-based interface that allows local and remote data entry and electronically confirms source data verification (electronic signature). C3D also provides researchers with web-based tools for ad-hoc querying, reporting and analysis of clinical data. DCI-IT has been a C3D adopter (locally hosted) for several years, and is the home of the caBIG Clinical Trials Management Systems Knowledge Center. Through this enhanced relationship, DCI-IT will have access to a wide range of tools and resources, including case report form templates, the Common Data Elements dictionary, and other global library elements. This will enable us to construct the necessary data collection tools quickly.

The process relies on the clinical site to originate data and correct any clinical data inconsistencies that are not included in the point of entry validation. A variety of quality control routines which are run regularly will spawn queries that will need to be addressed by the clinic in order for the record to be closed and made available for the analytic dataset. This cycle is key to the process, as depicted below:

THIS SPACE LEFT INTENTIONALLY BLANK

Electronic Case Report Forms (eCRF) will be generated from NCI/CaBIG and other templates and Common Data Elements (existing and specifically curated), most of which already exist in the caBIG C3D library.

Data entry via RDC Onsite is encrypted and secure. Communications between clinical sites that require this level of security will be handled via Tumbleweed's MailGate product (a 128 bit encrypted and authenticated e-mail system), as encapsulated through Duke's implementation of Microsoft's Outlook/Exchange Server product.

The eCRFs shown in Table 8 must be completed for all patients registered:

Table 8. Required eCRFs per each patients

[figure not shown]
Form and Reports	Due within		Copies	Comments
	Weeks	Event		
Initial On-Study Form	4	Registration	3	
Pre-Treatment Summary Form	4	Registration	3	The “prior therapy” form does not need to be completed
Solid Tumor Evaluation Form	4	Registration	3	
Primary disease: Pathology Form	6	Registration	3	
Pathology Report	6	Registration	4	
Slides	6	Registration		
Recurrent or Persistent Disease: Pathology Form	6	Registration	3	
Pathology Report	6	Registration	4	
Slides	6	Registration		
Cycle Drug Dose Form	2	Completion of each cycle of therapy	3	
Solid Tumor Evaluation Form	2	Clinical response assessment	3	
Common Toxicity Reporting Form	2	Beginning of each subsequent cycle	3	
Treatment Completion Form	2	Completion of study Rx and change in Rx	3	
Follow-up Form	2	Disease progression; death; normal follow-up	3	Quarterly for 2 years, semi-annually for an additional year for a total of 3 years

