4.1.9.2 Hepatic adverse events: The predominant dose limiting toxicity in phase I dose escalation trials was reversible elevation of hepatic transaminases, more pronounced for ALT than for AST. At doses below 200 mg bid no CTCAE grade 3+4 increases have been observed. According to phase II data, the probability to suffer from liver enzyme elevations of CTCAE grade 3 or 4 within the first two months of Nintedanib treatment is 10-15% for patients treated with 250 mg bid of Nintedanib. An increase of transaminases was only rarely observed in Caucasian patients treated with 150 mg bid or 200 mg bid. An association with hyperbilirubinemia was rare, and was (if at all) represented by a low grade increase of bilirubin with only one exception in a patient with tumor stenosis of the ductus hepatocholedochus and grade 3 bilirubin increase two weeks after cessation of therapy. γ -GT elevations, either as isolated increases or in combination with transaminitis, were observed frequently. Enzyme elevations generally normalized upon dose reduction or discontinuation. No drug-related hepatic failure was reported [8].

The current dose of Nintedanib in all studies is limited to 200 mg bid and, all studies require monitoring of liver enzyme tests. In addition, all studies include specific dose reduction schemes regarding liver enzyme elevations [8].

4.1.9.3 Infection adverse events: Infections have been observed but were expected for advanced cancer populations and age group. Only a few were considered drug related.

4.1.9.4 Thromboembolic and cardiac adverse events: In the combined phase I and II monotherapy trials (1199.1-3, 1199.9, 1199.10, 1199.11, 1199.16, 1199.19), there were 13 patients (3.7%) with events from the “selected thrombotic events” category which included pulmonary embolism (3), deep vein thrombosis (2), myocardial infarction (2), transient ischemic attack (2), aphasia (1), hemiparesis (1), thrombophlebitis (1), and thrombosis (1). Five of these events (1.4%) were considered treatment

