7.0 STUDY PARAMETERS

7.1 The following observations and tests are to be performed and recorded on the appropriate form(s). **Specimen requirements for translational research are provided in Section 7.3.**

Parameter	Pre-Therapy	Weekly	Prior to Each cycle	Every Other Cycle	Post Treatment Follow-up
History & Physical	X ¹		X		X
Performance Status	X ¹				
Clinical tumor measurement	X ¹		X ²		
Toxicity Assessment	X ³	X ⁷	X		
CBC/Differential/Platelets	X ³		X ⁴		X ¹⁰
Electrolytes, BUN, creatinine, Ca, Mg, PO ₄ , Urinalysis	X ³		X ⁴		X ¹⁰
Bilirubin, SGOT, SGPT, Alkaline Phosphatase	X ³		X ⁴		X ¹⁰
INR/PT/PTT ¹²	X ¹			X ¹²	
Serum Pregnancy Test (for patients of childbearing potential)	X ⁹				
Chest imaging (X-ray or CT scan of the chest)	X ¹			X ⁵	
Radiographic tumor measurement (RECIST)	X ^{1, 6}			X ⁶	X ⁶
Electrocardiogram (ECG)	X ¹			X ¹³	
CA-125	X ³		X ⁴		X
Capsule Diary			X ⁸		
Research samples	X ¹¹			X ¹¹	X ¹¹
Subject Preferences Tasks	X ¹⁴				
NFOSI-18	X ¹⁴				
FACT-GOG-Ntx	X ¹⁴				

Notes:

1. Must be obtained within 28 days prior to initiating protocol therapy.
2. For those patients whose disease can be evaluated by physical examination (i.e. nodes, pelvic mass).

3. Must be obtained within 14 days prior to initiating protocol therapy.
4. CBC/Differential/Platelets, liver function tests, creatinine, CA-125, and urinalysis must be obtained within 4 days before initiating the next cycle of treatment with protocol therapy.
5. Repeat chest imaging if initially abnormal or if required, to monitor tumor response.
6. CT scan or MRI if used to follow lesion for measurable disease every other cycle for the first 6 months; then every 3 months thereafter; and at any other time if clinically indicated based on symptoms or physical signs suggestive of progressive disease or rising serum tumor marker levels.
7. Nurse at site is to make weekly phone call to the patient during the **first two** cycles of treatment to inquire about any toxicity. The phone contact should be documented in the study participant's chart.
8. See Appendix II
9. If the patient is of child-bearing potential the serum pregnancy test must be obtained within 7 days prior to initiating protocol therapy.
10. These tests are to be done as needed at the discretion of the study doctor.

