11. See section 7.3 for specimen requirements. Collect whole blood, serum, plasma, and urine pre-cycle #1, every other cycle (i.e. Cycle 3, 5, etc.), at the time of progression, and one month after study treatment is discontinued.
12. Repeat every other cycle and more frequently as clinically indicated. For patients with hepatic injury or elevated liver function tests repeat the INR/PT/PTT every cycle until the liver function tests return to baseline; then resume INR/PT/PTT every other cycle.
13. Repeat every other cycle and more frequently as clinically indicated.
14. Only for subjects enrolled at Duke

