9.0 DURATION OF STUDY

- 9.0 Patients will receive therapy until disease progression or intolerable toxicity intervenes. The patient can refuse the study treatment at any time.
- 9.1 All patients will be treated (with completion of all required case report forms) until disease progression or study withdrawal. Patients will then be followed (with physical exams and histories) every three months for the first two years and then every six months for the next year. Patients will be followed for OS for up to 3 years after completing the study (due to either disease progression or study withdrawal).

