10.2 Reporting Period

Serious adverse events require immediate notification (within 24 hours of knowledge of the event) to [name] [name] of Duke University Medical Center or designated representative. The study period during which all AEs and SAEs must be reported begins after informed consent is obtained and initiation of study treatment on Cycle 1, Day 1. It ends 30 days following the last administration of study treatment, or if the patient initiates treatment with a new anti-cancer therapy, or study discontinuation/termination; whichever is earlier. Any SAEs occurring any time after this period should be promptly reported if a causal relationship to the investigational product is suspected; investigators should report only SAEs that are attributed to study treatment.

SAEs that are observed or reported prior to initiation of study treatment should be recorded as SAEs on the CRF if they are associated with protocol-mandated interventions (e.g., invasive procedures such as biopsies, medication washout, or no treatment run-in).

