suspended until all patients have been followed for at least 6 months or until at least 4 patients (15%) are found progression-free at 6 months. If 3 or less of the patients are progression-free at 6 months, the therapy will be deemed ineffective. If 4 or more of the patients are progression-free at 6 months, another 29 patients will be accrued. If 10 or less of the 56 patients are progression-free at 6 months, the therapy will be deemed ineffective. If at least 11 patients (20%) are progression-free at 6 months, the therapy will be deemed effective and worthy of further research. These stopping rules are illustrated in the table below.

Stage	Sample Size	Minimum number of patients who must be progression-free at 6-months for therapy to be considered effective
1	27	4 (15%)
2	56	11 (20%)

This design has a one-sided Type I error of 0.10, a power of 0.90. The probabilities of early termination given the null and the alternative are 0.54 and 0.04, respectively. If exactly 11 responses are observed, the exact 80% confidence interval will be [0.13, 0.28]. If even one patient drops out or is lost-to-follow-up before progression, then we will not be able to tabulate the number of patients who are progression-free at 6 months. In this case, we will calculate the Kaplan-Meier curve and focus on the probability of surviving to 6 months as calculated by the Kaplan-Meier method. We will call this trial a success only if the lower 10% confidence bound of this probability is greater than 0.13.

Statistical Analysis of Secondary Aims

Secondary Aim 1 is to determine the proportion of patient who has an objective tumor response (complete or partial). To address this aim all responses will be tabulated: complete response, partial response, stable disease, progressive disease.

Secondary Aim 2 is to determine the frequency and severity of adverse events. To address this aim, all toxicities will be tabulated by type and grade.

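### Section 10 requires adverse events to be recorded up to 30 days after the last dose, but Table 8 triggers no toxicity form for a patient's final cycle and the 7.1 schedule marks no toxicity assessment after treatment

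*Combined protocol and SAP*

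**What the plan says.** **The obligation.** The opening of section 10.0 has investigators assess adverse events at every evaluation and visit and record them on a CRF page. Section 10.2 sets the reporting window: "It ends 30 days following the last administration of study treatment", or at new anti-cancer therapy or study discontinuation or termination if that comes sooner. Section 10.3.8 puts every event, related or not, on an Adverse Reaction CRF. Section 10.11 repeats that serious and non-serious events are all collected.

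**The instruments.** Table 8 in section 10.14 lists the required eCRFs. The Common Toxicity Reporting Form is due 2 weeks after this event: "Beginning of each subsequent cycle". The Cycle Drug Dose Form in the same table is due 2 weeks after a different one: "Completion of each cycle of therapy". No Adverse Reaction CRF is listed.

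**The schedule.** In 7.1 the row "Toxicity Assessment" is marked pre-therapy, weekly (phone calls in the first two cycles, note 7) and before each cycle. It has no mark under post-treatment follow-up. Post-treatment blood counts, chemistry and liver tests are discretionary (note 10). Note 11 calls for research samples "at the time of progression, and one month after study treatment is discontinued". Section 9.1 then says: "Patients will then be followed (with physical exams and histories) every three months for the first two years".

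**The use.** Under Secondary Aim 2 in section 11, "all toxicities will be tabulated by type and grade".

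**The concern.** Section 10 sets a collection window, and the form list and visit schedule that sites work from stop short of it. A patient who stops during cycle k does not start cycle k + 1, so the event that makes the toxicity form due for cycle k does not occur. After that, no toxicity assessment is marked in 7.1, and section 9.1's follow-up visits run at three-month intervals.

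The affected interval is not a random part of follow-up. Sections 6.1 to 6.5 stop treatment permanently for repeated or persistent toxicity, and those events fall in the final cycle. If they are captured less completely than events in earlier cycles, the frequency and severity reported for objective 1.2.3 would tend to be too low. Late events can also occur: section 4.1.9.2 mentions a "grade 3 bilirubin increase two weeks after cessation of therapy". That patient had a tumour stenosis of the bile duct, so the case illustrates timing and not drug effect.

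**Working it through.** The documents give no figure for this point, so the main check is textual. A short calculation then gives a sense of scale.

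**1. Form trigger.** A patient who starts k cycles has k − 1 later cycle starts, so the trigger fires k − 1 times.
- k = 1: 0 forms triggered for 1 cycle.
- k = 2: 1 form for 2 cycles.
- In general one cycle per patient, always the last, has no due event. With up to 56 patients, that is up to 56 final cycles.

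The Cycle Drug Dose Form does not depend on a further cycle starting, so the dependence is particular to the toxicity form.

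**2. Window against schedule.**

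| Period | Section 10 requires | 7.1 marks toxicity | Table 8 triggers toxicity form |
|---|---|---|---|
| Cycles before the last | all events | yes | yes |
| Final cycle | all events | at its start; weekly calls if it is cycle 1 or 2 | no |
| Up to 30 days after last dose | all events | no | no |

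The only contact that 7.1 fixes near day 30 is the note 11 sample collection.

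**3. Other forms.** Table 8 also has a Treatment Completion Form and a Follow-up Form. Their contents are not described, so they can be assumed neither to capture graded toxicity nor to omit it.

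**4. Illustration of scale.** Inputs: 6-month PFS of 13% (null) and 27% (alternative) from section 11.3; 28-day cycles; a 30-day window. Assumption: time on treatment is exponential and ends at progression or death, with 6 months = 6 × 30.4375 = 182.625 days.

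- Daily hazard λ = −ln(p)/182.625. For p = 0.13, λ = 2.0402/182.625 = 0.01117. For p = 0.27, λ = 1.3093/182.625 = 0.00717.
- Probability of stopping within a given cycle = 1 − exp(−28λ) = 0.269 and 0.182. Of 56 patients, about 15 and 10 would stop in cycle 1.
- Mean cycles started = 1/0.2686 = 3.72 and 1/0.1819 = 5.50. The final cycle's share of all cycles started is the reciprocal, 27% and 18%.
- Mean time on treatment = 1/λ = 89.5 and 139.5 days, of which the final, incomplete cycle averages 13.3 and 13.5 days. Adding 30 days, the share of reporting time without a form trigger is (13.3 + 30)/(89.5 + 30) = 36% and (13.5 + 30)/(139.5 + 30) = 26%.

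Scheduled imaging is every other cycle (7.1, note 6), so actual stops for progression would cluster around imaging times. The cycle-1 share in particular depends on the model. The k − 1 count in step 1 does not.

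**The case against.** The strongest reply is that section 10 already requires this collection. Events are to be assessed at every visit (10.0), put on a CRF whatever their attribution (10.3.8) and reported to 30 days (10.2). The one-month sample contact is a natural occasion for that assessment. Patients withdrawn for adverse events are followed until the outcome is known (10.11). Serious events have a 24-hour route, and section 10.4 puts perforation, fistula, abscess and transaminase elevations on the same timeline. Cycles 1 and 2 have weekly toxicity calls. Section 10.14 says the Table 8 forms must be completed for all registered patients, which suggests that a patient who stops in cycle 1 still owes a toxicity form. The Aim 2 analysis is descriptive and the primary endpoint is untouched.

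Most of this stands, and it limits the point. A reader might infer that toxicity in the last cycle and the following 30 days goes uncollected, or that the window is missed for every patient. The documents do not support that: the obligation is explicit, and some contacts exist at which it can be met. Nor does every patient have a full 30-day window, because new therapy or study discontinuation can end it sooner.

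The reply does not close the gap in the instruments. A general duty to record is not a due date. The weekly calls are documented in the patient's chart, and no form is named for them. The CRF in 10.3.8 is absent from the list of required forms. The sentence introducing Table 8 says which forms are owed, not when one falls due for a cycle with no successor.

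**Conclusion.** The point holds as an inconsistency between section 10 and the tools meant to deliver it. Followed literally, Table 8 leaves each patient's final cycle without a triggered toxicity form, and 7.1 marks no toxicity assessment in the post-treatment part of the section 10.2 window. The exposure is mainly to non-serious events, including non-serious grade 3 events and some that led to stopping. The likely effect is under-capture in a descriptive secondary tabulation, of a size the documents do not allow one to estimate.

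The cycle-1 shares of 18% to 27%, and the 26% to 36% of reporting time, measure how much time lacks a trigger under an exponential assumption. They are not estimates of events lost and should not be read that way. The conclusion also assumes that the Treatment Completion and Follow-up Forms do not themselves collect graded toxicity; if they do, the gap is smaller. It is worth correcting because the correction is cheap.

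**What to change.** - **Table 8:** make the Common Toxicity Reporting Form due 2 weeks after the end of every cycle started, including the last or incomplete one, and once more at the end of the section 10.2 reporting window.
- **Section 7.1:** mark the toxicity assessment under post-treatment follow-up, at the progression and one-month contacts that note 11 already requires.
- **Sections 10.3.8 and 10.14:** reconcile the Adverse Reaction CRF with Table 8, by listing it or by stating that the Common Toxicity Reporting Form is that form.

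The cost is a changed form trigger, a schedule mark and about one extra form per patient. No new visit is needed, since the contacts for research samples are already planned.
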